6.7 Checklist and algorithm feasibility

The analysis of feasibility outcomes will be performed in the same way as the analysis of the clinical outcomes – that is, as descriptive statistics with corresponding 95% CIs. All feasibility outcomes are presented in Table 8.

6.8 Analysis of secondary (clinical) outcomes

Prior to algorithm-informed intervention(s):

The proportion of study participants for whom algorithm-informed management is indicated, and the proportion of study participants who decline indicated algorithm-informed management, will be estimated using the same approach taken for the descriptive analysis of the primary outcome(s).

Prior to and following algorithm-informed intervention:

PROMIS scores & Quality of Life scores

Means, standard deviations, and 95%CIs will be calculated for each PROMIS score (i.e., pain T-score, fatigue T-score, and bowel incontinence raw score) and EQ-5D-5L score will be calculated at initial checklist implementation (i.e., baseline) separately by whether intervention is indicated.

Following algorithm-informed intervention:

Change in PROMIS scores & Quality of Life scores

For study participants who receive algorithm-informed interventions for treatable causes of IBDrelated symptoms, PROMIS (for fatigue, pain, and faecal urgency/incontinence symptoms), IBD control score, and EQ-5D-5L scores three months after checklist implementation, after adjusting for relevant confounders, will be estimated. A linear regression model will be constructed for each outcome variable listed in appendix Table 6, adjusting for the baseline measure of that outcome variable, IBD diagnosis (e.g., Crohn's disease or other IBD type), and NHS Trust. Linear regression assumptions – for example, linearity, normally distributed error residuals, and residual homoscedasticity, and multi-collinearity – will be assessed. If data are normally distributed, a normal approximation will be used to estimate 95%CIs. If data are not normally distributed, bootstrap CIs will be estimated (using 1,000 bootstrap samples) because sample sizes may not be sufficiently large to invoke the central limit theorem. If regression models fail to converge, the covariate 'NHS Trust' will be removed.

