1.4 Development of the checklist and algorithm

Development work for this study has involved consulting a wide variety of gastroenterologists, IBD specialist nurses, patients and others. This work suggests that there is no current "standard of care" for investigating and treating these symptoms. Some clinics do very little while others conduct many different tests, with little consideration of costs or inconvenience to patients. Over an extensive series of interviews and group activities with stakeholders, there is now consensus on the contents of an algorithm for investigating and managing symptoms of fatigue pain and urgency/incontinence, with an accompanying preliminary self-completed checklist. During this development we have focussed on the common evidence-based causes (from our systematic reviews above) and interventions for our three symptoms (fatigue, pain, urgency), which consultees felt were also feasible for implementation in routine clinical practice. We have tried to achieve a balance between feasibility, costs and completeness. There were many other candidate tests, which were either not evidence-based or that patients and clinicians felt were too onerous to be part of routine clinical care for all patients with these symptoms.

3. Background and trial design

Study objectives	 To determine the proportion of participating IBD patients with fatigue, pain, and/or faecal urgency/incontinence who have pathophysiological contributors that are potentially medically treatable. To describe changes in symptoms three months after initiating algorithm-led management amongst patients with IBD-related symptoms and potentially reversible medical causes. To evaluate changes in health-related quality of life amongst patients with IBD-related symptoms starting algorithm-led management. To ascertain the feasibility of implementing IBD symptom checklist and algorithm in clinical practice. To determine what resources, such as costs, are incurred by the NHS during implementation of the algorithm.
	5. To qualitatively evaluate the experience and suggestions of
Study design	nurses implementing the algorithm. Multi-site, non-randomised, intervention study
Setting	Four NHS Trusts:
	 Barts Health NHS Trust (Royal London Hospital) Dorset County Hospital NHS Foundation Trust (Dorset County Hospital) London Northwest University Healthcare NHS Trust (St Mark's Hospital & Northwick Park Hospital)

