6.5 General analysis principles

Study participants who express desire for support with IBD-related symptoms and receive the selfreport symptom checklist will be included in descriptive baseline analyses. For study participants who receive algorithm-informed intervention(s), the effect size (e.g., mean change in symptom severity scores) will be estimated. A two-sided p-value and 5% alpha level will be used to declare

statistical significance. However, the focus of this analysis is descriptive. Ninety-five percent confidence intervals (95%Cls) will be reported unless stated otherwise.

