6.6 Analysis of the primary clinical outcomes

To fulfil the primary study objective, the proportion of study participants with (i) red flags, (ii) active IBD disease, (iii) blood test abnormalities (in participants with fatigue), (iv) irritable bowel syndrome or functional dyspepsia (in participants with pain), and (v) untreated loose stool (in participants with urgency) will be estimated. We will construct 95%CIs around proportion estimates using Wilson's Score Interval to minimize the loss of coverage that typically occurs with normal approximations of the Wald Interval. Complete case analyses (ignoring missing data) will be performed for primary outcomes.

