6.10 Subgroup analyses

A subgroup analysis will be performed that investigates the PROMIS scores (for pain intensity, fatigue, and bowel incontinence) at three months, and change in PROMIS scores for participants who receive the intervention, by disease type (Crohn's disease versus other IBD). Additionally, feasibility outcomes will be investigated by the four NHS Trusts/sites from which participants are recruited.

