6. EQ-5D-5L

Each of the five dimensions, mobility, self-care, usual activities, pain/discomfort, and anxiety/depression, comprising the EQ-5D descriptive system is divided into five levels of perceived problems:

LEVEL 1: indicating no problem LEVEL 2: indicating slight problems LEVEL 3: indicating moderate problems LEVEL 4: indicating severe problems LEVEL 5: indicating unable to/extreme problems A unique health state is defined by combining one level from each of the five dimensions. Levels 1-5 are coded as 1-5, respectively, and combining a level for each dimension gives a five-digit health state. These health states are then converted to an indexed value using the EQ-VT for England. The Index value set calculators are found on the Euroqol website and have been saved in the BOOST BCC folder as a Stata do file (Z:\STATISTICIANS\IBD-BOOST\EQ-5D-

Study IBD-BOOST OPTIMISE Document version 1.0

5L index value calculator). The EQ-VAS score is continuous and ranges from 1-100, with 100 indicating "the best health you can imagine" and 0 indicating "the worst health you can imagine." This score shows the patient's perceived overall health and requires no further derivation.

Requirements Specification Document Primary Clinical Outcomes

Clinical outcome – Abnormalities detected on blood test in people with fatigue

- Optimisation CRF: **130. fatiguenew D1.1**. Were new tests ordered for causes of fatigue? If that answer is YES and then **198. ftginterven E1.1.** Were interventions for fatigue advised or prescribed? If that is YES that means there was something abnormal.

Clinical outcome – Irritable Bowel Syndrome or functional dyspepsia indicated in people with pain (by responses on checklist)

- Optimisation CRF: **266. paininterven F1.1.** Were interventions for pain advised or prescribed? If that is a YES that means they had IBS or functional dyspepsia pain. We use a scoring system for these which I can send if helpful using the answers on the checklist. Redcap does this automatically. You can see this on the RSD section 3.7 questions 4 and 5.

Clinical outcome - Untreated loose stool detected in people with faecal urgency.

- Optimisation CRF - **280. urgencyadv G1.1. Were interventions for urgency advised or prescribed?** If this is a YES it means they had untreated urgency.

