Participants advised or prescribed interventions for fatigue	n (%)
Participants advised or prescribed interventions for pain	n (%)
Participants advised or prescribed interventions for faecal urgency	n (%)
Clinical intervention indicated by algorithm	n (%)
Algorithm-informed intervention declined	n (%)
*(faecal calprotectin test \geq 200 and/or IBD control score \leq	:13)

Table 5: PROMIS scores for pain, fatigue, and bowel incontinence at baseline and three months after checklist implementation in participants for whom algorithm-informed interventions were,

and were not, indicated

Outcome	Intervention indicated mean (SD)	No intervention indicated mean (SD)
PROMIS – Fatigue (T-Score)		
Baseline Three months		
PROMIS – Pain Intensity (T-Score)		
Baseline Three months		
PROMIS – Bowel Incontinence (Raw Score) Baseline Three months		
IBD-Control score (Raw Score)		
Baseline Three months		
IBD-Control VAS (Raw Score)		
Baseline Three months		
EQ-5D-5L Baseline Three months		
EQ-5D-5L VAS		
Baseline Three months		

Table 6: Number (n) and percentage (%) of missing data for PROMIS pain intensity, fatigue, and bowel incontinence scores at baseline and three months after checklist implementation in participants for whom algorithm-informed interventions were, and were not, indicated

Outcome	Intervention indicated n (%)	No intervention indicated n (%)
PROMIS – Fatigue (T-Score)		
Baseline		
Three months		
PROMIS – Pain Intensity (T-Score)		
Baseline		
Three months		
PROMIS – Bowel Incontinence (Raw Score)		
Baseline		
Three months		
IBD-Control score (Raw Score)		
Baseline		
Three months		
IBD-Control VAS (Raw Score)		
Baseline		
Three months		
EQ-5D-5L		
Baseline		
Three months		
EQ-5D-5L VAS		
Baseline		
Three months		

Table 7. Adjusted* mean PROMIS (pain, fatigue, and bowel incontinence) and EQ-5D-5L scores at three months after algorithm-informed interventions were indicated

Outcome	Intervention indicated mean (SD)	Missing n (%)
PROMIS – Fatigue (T-Score)*		
PROMIS – Pain Intensity (T-Score)*		
PROMIS – Bowel Incontinence (Raw Score)*		
IBD-Control score (Raw Score)*		
IBD-Control VAS (Raw Score)*		
EQ-5D-5L*		
EQ-5D-5L VAS*		

*adjusted for confounders: baseline measure for each outcome variable, inflammatory bowel disease diagnosis, and NHS

trust

Table 8 Total eligible sample size (N), and the number (n) and percentage (%) of participants completing outcomes on the feasibility of the self-report checklist and management algorithm

Ν	n (%)
	N

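### Three-month PROMIS scores are estimated only in a pooled any-intervention set; prespecify a symptom-matched estimate beside it

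*SAP*

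**What the plan says.** **Population.** Section 6.5 states the general rule: "For study participants who receive algorithm-informed intervention(s), the effect size (e.g., mean change in symptom severity scores) will be estimated". Section 6.8 applies it to the three-month scores: "For study participants who receive algorithm-informed interventions for treatable causes of IBDrelated symptoms, PROMIS (for fatigue, pain, and faecal urgency/incontinence symptoms". It then specifies the model: "A linear regression model will be constructed for each outcome variable listed in appendix Table 6". The covariates are the baseline score, IBD diagnosis and NHS Trust. None records which symptom was treated.

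**Tables.** Table 7 gives "scores at three months after algorithm-informed interventions were indicated", with one column for all seven outcomes. Table 9 does the same, split by disease type. That split is the only subgroup planned for these scores (section 6.10): "change in PROMIS scores for participants who receive the intervention, by disease type (Crohn's disease versus other IBD".

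**Objective.** The second study objective (section 3) is "To describe changes in symptoms three months after initiating algorithm-led management amongst patients with IBD-related symptoms and potentially reversible medical causes".

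**Where the plan does match by symptom.** Section 6.6 ties the primary clinical outcomes to the relevant symptom, for example "blood test abnormalities (in participants with fatigue), (iv) irritable bowel syndrome or functional dyspepsia (in participants with pain", and does the same for loose stool in participants with urgency. Appendix 2 names a separate CRF item for each symptom. The fatigue item (E1.1) asks "Were interventions for fatigue advised or prescribed"; F1.1 and G1.1 are the counterparts for pain and urgency.

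**The concern.** Three of the routes in section 4.1 are symptom-specific: fatigue through blood test abnormalities, pain through irritable bowel syndrome or functional dyspepsia, and urgency through untreated loose stool. Participants need not have all three symptoms, since section 5.1 counts people with one or more. So a person treated only for loose stool enters the fatigue and pain regressions. If that person has no fatigue or pain, the baseline score is at the floor (raw 4 or raw 3) and can only stay there or worsen.

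The Rationale in the Introduction says it is unclear whether symptoms respond to correcting biomedical abnormalities. To describe that, the symptom must correspond to the abnormality addressed. The pooled mean mixes targeted and untargeted participants in proportions that the tables do not show and that may differ between the three scales. A response among those treated could look small for that reason alone. A matched analysis added after the results are known would be post hoc under section 1.5.

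**Working it through.** **1. The plan's own figure.** The only precision figure in the SAP is the maximum 95% CI width of 13.9% for a proportion with 200 participants (section 5.1a). It reproduces: 2 × 1.96 × √(0.25/200) = 0.1386. It does not concern the three-month scores.

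**2. Inputs.** The SAP gives no share treated for each symptom, no expected change and no SD of change. Assumptions:
- q, the share of the pooled set treated for the symptom: 20% to 90%
- d, the improvement in those treated for it: 5 T-score points
- s, the improvement in the rest: 0, or one third of d (5/3)
- 100 recipients, with an SD of change of 8 or 10, the same in both groups

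The T-score figures apply to fatigue and pain. Bowel incontinence has only a raw score (Appendix 2).

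**3. Dilution.** Pooled mean change = q·d + (1 − q)·s.

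| q | s = 0 | s = 5/3 |
|---|---|---|
| 20% | 1.0 | 2.3 |
| 40% | 2.0 | 3.0 |
| 60% | 3.0 | 3.7 |
| 80% | 4.0 | 4.3 |
| 90% | 4.5 | 4.7 |

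The matched mean is 5 in every row. The Introduction's remission prevalences can stand in for q as an illustration only, because they are symptom frequencies and not treatment shares. With s = 0, fatigue would show 0.41 × 5 ≈ 2.1 and pain 0.62 × 5 = 3.1. Incontinence would keep up to 75% of its raw-score change.

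**4. Price of matching.** 95% CI half-width = 1.96 × SD/√n.

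| n | SD 8 | SD 10 |
|---|---|---|
| 100 (pooled) | 1.57 | 1.96 |
| 80 | 1.75 | 2.19 |
| 60 | 2.02 | 2.53 |
| 40 | 2.48 | 3.10 |
| 20 | 3.51 | 4.38 |

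**5. Which estimate stands out more from its noise.** Take q = 1/3, SD 8 and 100 recipients, 33 of them matched.
- Matched: 5/(8/√33) = 5/1.39 = 3.6
- Pooled, s = 0: 1.67/0.8 = 2.1
- Pooled, s = 5/3: 2.78/0.8 = 3.5
- Pooled, s = 2.5: 3.33/0.8 = 4.2

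The two are equal at s = d√q/(1 + √q) = 5 × 0.577/1.577 ≈ 1.8 points. Above that, pooling has the better ratio.

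**The case against.** **The pooled set fits the stated objective.** The second objective concerns algorithm-led management in people with symptoms and potentially reversible causes, and it is not worded per symptom. A reader might infer that section 6.8 contradicts it. The SAP does not support that reading: a pooled set is a fair way to describe the algorithm as a whole. This part of the objection stands.

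**Active disease is a fourth route.** Section 4.1 lists active disease among what is detected, and section 6.3 bars further OPTIMISE intervention for red flags but not for active disease. The SAP does not say how active disease is managed, but such management could plausibly affect all three symptoms. It is therefore not established that nothing was done for the untargeted symptoms. Anyone managed only for active disease would also drop out of every matched set. This stands, and it is a reason to keep the pooled analysis.

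**A matched analysis has weaknesses of its own.** There is no control group, and selecting people on a symptom invites regression to the mean. A reader might also infer that matching gives the clearer signal. Step 5 shows that this depends on how much the others improve, and the order can reverse.

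**The setting is modest.** These are secondary outcomes in a study refocused on feasibility. Section 6.5 calls the analysis descriptive, and the SAP plans no comparison between the three symptoms. That limits the harm. It does not supply the missing estimate: nothing in the plan would show how fatigue changed in those treated for fatigue, or pain or incontinence in their counterparts.

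**Conclusion.** The point holds as a gap in what is reported. It is not an error in the pooled analysis. Each three-month PROMIS score is estimated only among people with any intervention, so the plan cannot describe symptom change in those treated for that symptom, which is what the Rationale asks about. Adjusting for the baseline score does not remove the mixing.

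The direction is known only conditionally: the pooled mean lies below the matched mean whenever untargeted participants improve less. The amount cannot be fixed from the SAP. Under the assumptions above, a 5-point change appears as anything from 1.0 to 4.7 points. Dilution shrinks if symptoms overlap heavily or if management of active disease improves all three.

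The SAP does not support replacing the pooled analysis, and the point does not extend to IBD-Control or EQ-5D-5L, which are global measures. Adding matched estimates beside the pooled ones is a cheap improvement using data already planned.

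**What to change.** In section 6.8 and Tables 7 and 9, keep the pooled analysis and prespecify beside it a symptom-matched estimate for each PROMIS scale, with n and 95% CI:

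- **Fatigue:** participants meeting the Appendix 2 fatigue derivation (D1.1 = YES and E1.1 = YES).
- **Pain intensity:** participants with F1.1 = YES.
- **Bowel incontinence:** participants with G1.1 = YES.

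Report participants managed only for active disease in the pooled set, and say so. Leave IBD-Control and EQ-5D-5L pooled. State that the CRF items record interventions advised or prescribed, and reconcile this with section 6.8, which refers to participants who receive interventions, and with the tables, which refer to interventions indicated. The table wording could admit people who declined. Label the matched estimates as descriptive, uncontrolled before-after change that is open to regression to the mean.

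The cost is SAP wording and extra table columns, with no new data collection. The matched sets will be smaller and their intervals wider: under the assumptions above, with 100 recipients and 40 matched, the half-width rises from 1.57 to 2.48 points (SD 8) or from 1.96 to 3.10 (SD 10).

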	 St Helens and Knowsley Teaching Hospitals NHS Trust (Whiston Hospital or St Helen's Hospital)
Participants	Adults with IBD who have completed the IBD-BOOST survey at stage 2 of the Programme Grant and have indicated on that survey that they would like further support for their symptoms Number of participants 200
	 Inclusion criteria Diagnosis of IBD (including patients with an ileo-anal pouch or stoma) 18 years and over Lives in UK and attends one of the IBD-BOOST clinical sites for routine IBD care Has completed the IBD-BOOST survey (stage 2 of Programme Grant) and indicated that they would like further support to help manage their symptoms Ability to give informed consent and sufficient command of English to understand study documents and procedures will be assumed from response to the previous survey

	Exclusion criteria		
	Under 18 years		
Interventions	Study participants will complete a self-report symptom checklist and provide a stool sample. A healthcare professional from their clinical site will review checklist responses using an agreed algorithm and offer to initiate additional tests or clinical management as indicated by the algorithm. There is no control group in this non-randomised, intervention study.		
Primary outcome	Feasibility outcomes		
measure(s)	 Proportion of consenting participants who: (i) completed the symptom checklist (ii) returned the postal faecal calprotectin test Proportion of participants for whom, after returning both the symptom checklist and faecal calprotectin test, no algorithm-informed action was indicated (and thus could progress to the RCT) Proportion of participants for whom algorithm-informed action was indicated where the clinical team completed and returned the CRF (to indicate the actions they planned) Of participants where algorithm-informed actions were indicated, the proportion who completed outcome measures at three months (i.e., attrition rates). Number and proportion of participants consenting to receive the algorithm-informed intervention but then discontinuing (with reasons if possible). 		

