- EQ-5D-5L score

Table 9: Subgroup analysis - adjusted mean PROMIS (pain, fatigue, and bowel incontinence) andEQ-5D-5L scores at three months after algorithm-informed interventions were indicated, stratifiedby Inflammatory Bowell Disease type

	Algorithm-informed int	thm-informed intervention indicated	
Outcome	Crohn's disease	Other IBD	
	(n=X)	(n=Y)	
PROMIS – Fatigue (T-Score)*	mean (SD)	mean (SD)	
PROMIS – Pain Intensity (T-Score)*	mean (SD)	mean (SD)	
PROMIS – Bowel Incontinence (Raw Score)*	mean (SD)	mean (SD)	
IBD-Control score (Raw Score)*	mean (SD)	mean (SD)	
IBD-Control VAS (Raw Score)*	mean (SD)	mean (SD)	
EQ-5D-5L*	mean (SD)	mean (SD)	

*adjusted for confounders: baseline measure for each outcome variable, inflammatory bowel disease diagnosis, and NHS

trust

Table 10: Sensitivity analysis: multiple imputation of primary outcomes

Outcome	n (%) (complete case data)	n (%) (multiply imputed data)	
At least one red flag on self-report checklist			
Active disease*			
Participants advised or prescribed interventions for fatigue			
Participants advised or prescribed interventions for pain			
Participants advised or prescribed interventions for urgency

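### The SAP promises change in symptom scores at three months, but its model and tables deliver only a three-month level, and no estimator or interval for change is specified

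*SAP*

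**What the plan says.** Section 3 (study objectives) sets the aim: "To describe changes in symptoms three months after initiating algorithm-led management amongst patients with IBD-related symptoms" and potentially reversible medical causes. The same table states: "There is no control group in this non-randomised, intervention study". Section 6.5 gives mean change in symptom severity as its example of the effect size. Section 6.10 includes change in PROMIS scores by disease type.

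The modelling text in section 6.8 sits under a subheading on change. It is restricted as follows: "For study participants who receive algorithm-informed interventions for treatable causes of IBDrelated symptoms". What it then estimates is the three-month score after adjustment: "A linear regression model will be constructed for each outcome variable listed in appendix Table 6, adjusting for the baseline measure" of that outcome, IBD diagnosis and NHS Trust. It plans 95% CIs by normal approximation or 1,000 bootstrap samples.

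Table 7 is titled: "Adjusted* mean PROMIS (pain, fatigue, and bowel incontinence) and EQ-5D-5L scores at three months after algorithm-informed interventions were indicated". Its result column is mean (SD). Table 9 repeats this by IBD type. The footnote to both reads: "adjusted for confounders: baseline measure for each outcome variable, inflammatory bowel disease diagnosis, and NHS" trust.

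Table 5 gives baseline and three-month means (SD) separately, and section 7 plans line graphs of both, with 95% CIs, for the three PROMIS scores. Section 6.5 also says: "A two-sided p-value and 5% alpha level will be used to declare" statistical significance, and then that the focus is descriptive.

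**The concern.** A model described as serving an analysis of change has no change in it. The outcome is the later score, everyone in the model receives the intervention, and no coefficient compares groups or time points. With no exposure contrast there is nothing for diagnosis, Trust or baseline to confound, so the label in the table footnotes does not fit.

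Two things are at stake. The effect size for a named objective is left to be chosen when the data are in hand. And Tables 7 and 9 may be read as confounder-adjusted evidence about the intervention when they contain a three-month average. If some participants do not return the three-month questionnaire, subtracting the two means in Table 5 may compare different sets of people, so differential non-response could pass for change. Attrition is itself a feasibility outcome in section 4, and the multiple imputation in section 6.11 is set up for the primary clinical outcomes, not for these scores.

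**Working it through.** The SAP gives no figure on this point. Its only precision statement, a maximum 95% CI width of 13.9% for a proportion with n = 200 (section 5.1a), reproduces as 2 × 1.96 × √(0.25/200) = 0.1386, but has no bearing on change.

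**1. What is promised and what is specified**

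| Place | Quantity |
|---|---|
| Objective 2, section 3 | change at three months |
| Section 6.5 | mean change as effect size, no method |
| Section 6.8, subheading | change |
| Section 6.8, model | three-month score given baseline, diagnosis, Trust |
| Section 6.10 | three-month scores and change, by disease type |
| Tables 7 and 9 | adjusted three-month mean (SD) |
| Table 5, line graphs | separate means at each time |

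No row gives an estimator, an interval or a table cell for within-person change.

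**2. The identity.** In least squares with an intercept the residuals sum to zero, so ȳ = x̄′β̂. The prediction at the covariate means of the analysed participants, or averaged over them, is the raw three-month mean.

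**3. Numerical check.** The SAP gives none of these inputs, so all are assumed for illustration: 100 treated participants, baseline mean near 60 and SD 10, slope on baseline 0.6, residual SD 8, four Trusts of unequal size, modest Trust and diagnosis effects, and shifts of 0, −3 and −6.

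| Assumed shift | Raw three-month mean | Adjusted mean | Baseline mean | Mean paired change | Same, all baselines +5 |
|---|---|---|---|---|---|
| 0 | 59.423 | 59.423 | 59.510 | −0.09 | −5.09 |
| −3 | 56.325 | 56.325 | 60.294 | −3.97 | −8.97 |
| −6 | 54.748 | 54.748 | 60.704 | −5.96 | −10.96 |

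Raw and adjusted means agree to about 1e-14. Adding 5 to every baseline left the adjusted mean where it was and moved change by 5. The adjusted mean alone carries no information on change.

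**4. Other evaluation points.** The SAP does not say at which covariate values the adjusted mean is taken. Equal weights on Trusts and diagnoses gave 57.65, 53.60 and 54.21. With three-month data missing in relation to baseline, averaging over all treated participants gave 59.02, against a completer mean of 56.28 (first set). These differ from the raw mean but are still levels.

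**5. Precision of change.** Regressing the change score on the same covariates returns the mean paired change as its average prediction. The model SE, residual SD/√n, was 0.72, 0.84 and 0.87; the paired SE was 0.84, 1.06 and 0.92. The model SE treats the baseline mean as fixed. Analytically, assuming n = 80, SD 10 and retest correlation 0.7: model SE = 10√(1 − 0.49)/√80 = 7.14/8.94 = 0.80; paired SE = 10√(2 × 0.3)/√80 = 7.75/8.94 = 0.87.

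**6. Why a significance rule on change would mislead.** No pre-post test is specified, so this bears only on a test that might be added. If the sample mean lies d points above the mean of its source population and retest correlation is r, expected drift with no treatment effect is (1 − r)d. With n = 80 and SD 10, the chance of p < 0.05 is about P(Z > 1.99 − drift/SE). At r = 0.7, d = 5: drift 1.5, 1.5/0.866 = 1.73, about 40%. At r = 0.7, d = 10: drift 3, 3/0.866 = 3.46, about 93%. Over r from 0.5 to 0.8 and d from 5 to 10 it runs from about 28% to 99%. The inputs are assumptions, and the range is too wide to support any single figure.

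**The case against.** The objective is only to describe change. Section 6.5 says an effect size such as mean change will be estimated, Table 5 and the graphs show both time points, section 6.8 does plan 95% CIs, and section 6.1 calls the appendix tables drafts. On this view a missing column is a drafting gap. Much of that stands. A reader might infer that objective 2 cannot be answered, but a crude difference is available. The SD heading in Tables 7 and 9 is a slip against text that plans intervals. What does not stand is that this settles the matter: those intervals attach to a three-month level, and describing change still needs a defined statistic.

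Four other inferences go further than the document allows.
- That the adjusted mean always equals the raw mean. It does so only at the covariate means of the analysed cases; step 4 shows that adjustment can matter when follow-up is incomplete.
- That Table 9 wrongly adjusts for diagnosis within strata where it is constant. Section 6.10 does not require separate models, and one model containing diagnosis can yield both means.
- That the plan will declare a spurious improvement. It names no pre-post test and says the focus is descriptive. Entry is by a wish for support, not a score threshold, and the relevant source mean is that of IBD survey respondents, which the SAP does not give.
- That Table 5 uses available cases. The SAP does not say, and Table 6 does report missingness by time point.

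**Conclusion.** The gap is real. The SAP promises mean change in several places and specifies it in none; the section 6.8 model and Tables 7 and 9 yield a three-month level without a contrast. This follows from the form of the model and needs no assumed figures. The simulated values only illustrate it, and equality with the raw mean depends on where the adjusted mean is evaluated. The outcomes are secondary, the study has been converted to a feasibility study, and no primary result depends on them, so it is a should-fix.

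The model sentence also points to Table 6, a missing-data table, while its results belong in Table 7. The two list the same seven measures, so the slip does not alter which models are fitted.

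**What to change.** - In section 6.8, define the estimand as mean within-person change, three months minus baseline, with a 95% CI. Estimate it from paired differences in participants with both measurements, using a paired or bootstrap SE, or from a repeated-measures mixed model using all observed baseline and three-month scores. Do not use the model SE of a centred-covariate intercept, which is too narrow.
- In Tables 7 and 9, replace the adjusted mean (SD) with mean change (95% CI), and drop the confounder wording from the footnotes.
- Report change by disease type from one model.
- Correct the reference to Table 6.
- State in section 6.5 that uncontrolled pre-post change is not a treatment effect and that no significance will be declared on it.

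The cost is SAP wording and two table shells, with no new data. The small loss is that significance claims on change are given up.
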